### 6.2.4 Intrasubject Dose Escalation

Intrasubject dose escalation is not allowed in this trial and each subject will stay on the assigned dose level (except for dose modification due to tolerability) throughout his/her treatment period unless there is a considerable reason to allow intrasubject dose escalation. Any intrasubject dose escalation must be agreed by the sponsor.

# 6.3 Assignment to Treatment Groups

Not applicable; all subjects will receive MSC2156119J. Subjects will be enrolled into the appropriate dose cohort and part of the trial being enrolled at the time.

#### Subject Number

The subject number will consist of a 4-digit site number followed by a 4-digit subject number in ascending order (e.g., Subject 0102-0001 is the first subject at Site 0102). The first 2 digits of the site number indicate the country. For subjects participating in Phase II, 2000 will be added to the subject number (e.g., Subject 0102-2001 is the first subject in Phase II at site 0102).

Subject numbers will not be reassigned to other subjects or reused in this trial. If a subject is replaced, the replacement will be enrolled with a unique subject number.

# 6.4 Other Drugs to be Used in the Trial

Not applicable.

# 6.5 Concomitant Medications and Therapies

## 6.5.1 Permitted Medicines

Any medications (other than those excluded by the clinical trial protocol) that are considered necessary for the subjects' welfare and will not interfere with the trial medication may be given at the investigator's discretion.

The investigator will record all concomitant medications/procedures taken by the subject during the trial, from the date of signature of informed consent, in the appropriate section of the eCRF.

Any additional concomitant therapy that becomes necessary during the trial and any change to concomitant drugs must be recorded in the corresponding section of the eCRF, noting the name, dose, duration and indication of each drug.

The following are permitted:

- Oral antivirals for chronic hepatitis are permitted either prior to or during the trial;
- Ongoing interferon therapy for hepatitis started before entering the trial; and
- Concomitant medications that have a narrow therapeutic window and are known to be transported by P-gp (e.g., rivaroxaban, apixaban, ranolazine, talinolol, digoxin), BCRP (e.g., rosuvastatin), or OCT1 are permitted, but should be used with caution.
- Concomitant medications that are known to inhibit P-gp (e.g. itraconazole, telaprevir, clarithromycin, ketoconazole, and conivaptan) are permitted, but should be used with caution.

The investigator may decide not to include a subject in the trial, if the subject cannot withdraw the drugs that have a narrow therapeutic range and that are known to be transported via P-gp; If the investigator decides to enroll a subject who is treated with a drug that is transported via P-gp, BCRP or OCTI and has a narrow therapeutic range, close safety monitoring is advised.

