### 5.3.2 Exclusion Criteria

Subjects are not eligible if they fulfill any of the following criteria:

1. Prior systemic anticancer treatment for advanced HCC (except for sorafenib as described in the inclusion criteria);

Document No. CCI Object No. CCI

- 2. Prior treatment with any agent targeting the HGF/c-Met pathway;
- 3. Local-regional therapy within 4 weeks before Day 1 (for example, surgery, radiation therapy, hepatic arterial embolization, transcatheter arterial chemoembolization [TACE], chemoembolization, radiofrequency ablation, percutaneous ethanol injection, cryoablation);
- 4. Laboratory index at baseline:
  - Hemoglobin  $\leq 8.5$  g/dl;
  - Neutrophils  $< 1.5 \times 10^9$ /L;
  - Platelets  $< 60 \times 10^9$ /L;
  - Total bilirubin > 3 mg/dl;
  - Aspartate aminotransferase (AST) or alanine aminotransferase (ALT) > 5 x upper limit of normal (ULN);
  - Serum creatinine  $\geq 1.5 \text{ x ULN}$ ;
  - Calculated creatinine clearance < 60 ml/min according to the Cockcroft-Gault formula;
  - International normalized ratio (INR) > 2.3;
- 5. Past or current history of neoplasm other than HCC, except for curatively treated nonmelanoma skin cancer, in situ carcinoma of the cervix, or other cancer curatively treated and with no evidence of disease for at least 5 years;
- 6. Known central nervous system (CNS) or brain metastasis that is either symptomatic or untreated;
- 7. Medical history of difficulty swallowing, malabsorption or other chronic gastrointestinal disease, or conditions that may hamper compliance and/or absorption of the tested products;
- 8. Clinically significant gastrointestinal bleeding within 4 weeks before trial entry;
- 9. Peripheral neuropathy Grade ≥ 2 (Common Terminology Criteria for Adverse Events [CTCAE] v 4.0);
- 10. Impaired cardiac function evidenced by any of the following conditions:
  - left ventricular ejection fraction (LVEF) < 45% defined by echocardiograph (screening assessment is not required for subjects without a history of congestive heart failure unless clinically indicated);
  - serious arrhythmia;
  - unstable angina pectoris;

Document No. CC Object No. CC

- myocardial infarction within the last 12 months prior to trial entry, or pericardial effusion;
- Subjects with a QTc-prolongation > 470 msec, risk factors for Torsades de Pointes (Heart Insufficiency NYHA II-IV (Appendix B), Hypokalemia, Family Long-QT-Syndrome) should be excluded from the study.

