- 11. Uncontrolled hypertension by standard medication (not stabilized to 150/90 mmHg or below);
- 12. Known human immunodeficiency virus (HIV) infection;
- 13. Known or suspected drug hypersensitivity to any ingredients of MSC2156119J;
- 14. Female subjects who are not of childbearing potential due to being postmenopausal (2 years without menses) or surgical sterilisation (oophorectomy, hysterectomy and/or tubal ligation) do not need to use contraception.

All other female subjects are considered to have childbearing potential. These female subjects, as well as childbearing female partners of male subjects, are to use highly effective methods of contraception – defined as one that results in a failure rate of less than 1% per year when used consistently and correctly - throughout the study (from screening until 3 months after last dose of trial medication).

Examples are combined oral contraceptives, intrauterine devices, implantable or injectable hormonal contraceptives together with a barrier method.

In addition, male subjects should use adequate contraception throughout the study (e.g. condom and spermicidal jelly).

Female subjects must have a negative pregnancy test ( $\beta$ -HCG test in serum) prior to enrollment;

- 15. Concurrent treatment with non-permitted drug per principal investigator and the Merck Serono medical monitor, in accordance with Section 6.5.2 of the protocol;
- 16. Substance abuse, other acute or chronic medical or psychiatric condition or laboratory abnormalities that might increase the risk associated with trial participation at the discretion of investigators;
- 17. Prior treatment with MSC2156119J or other c-Met inhibitors;
- 18. Participation in another interventional clinical trial within the 28 days prior to Day 1;
- 19. Previous anticancer treatment-related toxicities not recovered to Grade 0-1 or baseline (except alopecia, peripheral neuropathy, and elevated liver enzymes);

20. History of liver transplant;

Document No. CC Object No. CC

- 21. Active or uncontrolled infections except chronic HBV, chronic HCV, or both;
- 22. Subjects with any concurrent medical condition or disease that will potentially compromise the conduct of the trial at the discretion of the investigators.

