# 5.5.2 Withdrawal from MSC2156119J

The subject must be withdrawn in the event of any of the following:

- Occurrence of an exclusion criterion which is clinically relevant and affects the subject's safety, if discontinuation is considered necessary by the investigator and/or sponsor;
- Therapeutic failure (i.e., oncologic emergency due to serious tumor progression or serious side effect) requiring urgent additional drug;
- QTc >500 msec or change of QTc from Baseline > 60 msec;
- Occurrence of AEs, if discontinuation of trial drug is desired or considered necessary by the investigator and/or the subject;
- Occurrence of pregnancy;
- Use of a non-permitted concomitant drug, as defined in Section 6.5.2, where the predefined consequence is withdrawal from MSC2156119J;
- Non-compliance with administration of MSC2156119J;
- Documented progression of the disease;
- Initiation of any other anticancer treatment (including radiotherapy, surgery, hormonal therapy).

If a subject withdraws from MSC2156119J, every effort should be made to document objective progression even after discontinuation of treatment. Subjects who discontinue trial treatment for reasons other than disease progression or withdrawal of consent will continue to have tumor assessments according to the same schedule as subjects who remain on the trial treatment. These assessments will continue until disease progression, withdrawal of consent, starting a new anticancer therapy, or death.

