### 6.5.2 Non-permitted Medicines

Any additional concomitant therapy that becomes necessary during the trial and any change to concomitant drugs must be recorded in the corresponding section of the eCRF, noting the name, dose, duration and indication of each drug.

The following are not permitted during the trial:

- Initiation of new interferon therapy for hepatitis within 30 days prior to Day 1 or at any time during the trial;
- Any other cancer therapy, including chemotherapy or local regional treatments, or any investigational product other than MSC2156119J as defined in this protocol;
- Prophylactic granulocyte colony stimulating factor (G-CSF) or granulocyte-macrophage colony stimulating factor (GM-CSF);

- Drug(s), for which the package insert/summary of product characteristics includes a contraindication for P-gp (e.g., dabigatran, aliskiren, colchicine), BCRP, and/or OCT1 inhibiting drugs, must not be combined with MSC2156119J;
- Drug(s) that are known to induce P-gp and thereby may decrease efficacy of MSC2156119J such as drugs known to induce P-gp (e.g., avasimibe, carbamazepine, phenytoin, rifampin, Saint John's wort);
- Subjects who receive a drug that is known to prolong QTc interval and cause respective cardiac side effects (see Appendix L).

Use of non-permitted medicines for any reason must result in withdrawal of the subject from this trial.

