# Appendix L: Examples of Drugs that Prolong QT Interval and Have a Risk of Torsades de Pointe

The following lists provide examples of drugs that prolong QT Interval and have a risk of Torsades de Pointe (http://crediblemeds.org/). Please note the following: This is not an exhaustive list. If you have questions on a drug product not included in this list, please consult the prescribing information for that product.

Amiodarone	Sparfloxacin
Anagrelide	Haloperidol
Arsenic trioxide	Halofantrine
Astemizole	Ibutilide
Azithromycin	Levomethadyl
Bepridil	Mesoridazine
Chloroquine	Methadone
Chlorpromazine	Moxifloxacin
Cisapride	Ondansetron
Citalopram	Pentamidine
Clarithromycin	Pimozide
Cocaine	Probucol
Disopyramide	Procainamide
Dofetilide	Quinidine
Domperidone	Sevoflurane
Dronedarone	Sotalol
Droperidol	Sulpiride
Erythromycin	Terfenadine
Escitalopram	Thioridazine
Flecainide	Vandetanib

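### Protocol Section 6.5.1 permits clarithromycin by name, while Section 6.5.2 with Appendix L prohibits it as a QT-prolonging drug and requires withdrawal for its use

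*Protocol*

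**What the plan says.** Section 6.5.1 of the protocol opens with a general permission for medicines that the investigator thinks necessary, leaving out any that the protocol excludes. A list of permitted medicines follows. One entry covers drugs with a narrow therapeutic window that are transported by P-gp, BCRP or OCT1. The next covers concomitant medicines "known to inhibit P-gp (e.g. itraconazole, telaprevir, clarithromycin, ketoconazole, and conivaptan) are permitted, but should be used with caution".

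Section 6.5.2 lists what is not permitted. Its last entry is phrased as a class of subject but plainly means a class of drug: "Subjects who receive a drug that is known to prolong QTc interval and cause respective cardiac side effects (see Appendix L". The section then states the consequence: "Use of non-permitted medicines for any reason must result in withdrawal of the subject from this trial". Appendix L is headed "Examples of Drugs that Prolong QT Interval and Have a Risk of Torsades de Pointe", and one of its entries is "Clarithromycin".

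Four other provisions bear on the point:

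- Exclusion criterion 15 (Section 5.3.2) bars concurrent non-permitted treatment "in accordance with Section 6.5.2 of the protocol".
- Exclusion criterion 10 keeps out "Subjects with a QTc-prolongation > 470 msec, risk factors for Torsades de Pointes".
- Section 5.5.2 stops the trial drug for "QTc >500 msec or change of QTc from Baseline > 60 msec".
- Appendix 1 of both SAPs (Phase Ib and Phase II) has a deviation code, PDEV32, for subjects who took a non-permitted medicine and were not withdrawn. It refers to Section 6.5.2 and requires medical review.

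**The concern.** Someone checking whether clarithromycin is allowed will find it by name in the permitted list. Nothing in that entry points to Section 6.5.2 or Appendix L, and nothing in it mentions QT.

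Two things are at stake. The first is safety: a site could give a drug that the protocol bars for its cardiac risk. The second is conduct: the same prescription is allowed by one section and triggers mandatory withdrawal under the next, so a subject could lose the trial treatment because the site followed a named permission. If the site did not withdraw the subject, medical review for PDEV32 would have to apply two texts that disagree.

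**Working it through.** The plan gives no figure to reproduce here. The check is a comparison of current protocol text, followed by a count of names.

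**Status of clarithromycin in each place**

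- Section 6.5.1: permitted, with caution, as a named P-gp inhibitor.
- Section 6.5.2: not permitted if it falls in the QTc-prolonging class illustrated by Appendix L.
- Appendix L: named, so it does fall in that class.
- Section 6.5.2, closing sentence: any use leads to withdrawal from the trial.

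The first status contradicts the other three.

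**Overlap of the two lists**

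- Named in Section 6.5.1: 5 P-gp substrates (rivaroxaban, apixaban, ranolazine, talinolol, digoxin) + 1 BCRP substrate (rosuvastatin) + 5 P-gp inhibitors (itraconazole, telaprevir, clarithromycin, ketoconazole, conivaptan) = 11.
- Named in Appendix L: 20 rows × 2 columns = 40.
- In both: 0 of 6 substrates and 1 of 5 inhibitors, so 1 of 11, which is clarithromycin.

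Both lists are only examples, and Appendix L says that it is not exhaustive. The result is therefore a count of named overlap. It does not show that the other ten drugs, or unnamed members of the permitted classes, are free of the same conflict.

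**When the conflict bites**

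- At entry, criterion 15 makes Section 6.5.2 the governing text, so clarithromycin should be caught.
- On treatment, no such pointer exists. A new prescription is checked against Sections 6.5.1 and 6.5.2 directly, and they disagree.

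**What the other safeguards cover**

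- Criterion 10 acts once, before treatment.
- Potassium and magnesium are in the chemistry panel (Table 2), and ECGs are taken in triplicate (Section 7.4.4.4). Both follow the visit schedule and are not prompted by starting a new drug. Under Section 7.1.3.7, visits are every 3 weeks through Cycle 8, every 6 weeks from Cycle 9 and every 12 weeks after Cycle 13. Extra ECGs are at the investigator's discretion (Appendices G and H).
- The stopping rule in Section 5.5.2 acts only after prolongation has been seen.

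**The case against.** The strongest reply is that the protocol already settles the matter. The opening sentence of Section 6.5.1 leaves out anything excluded elsewhere, criterion 15 makes Section 6.5.2 govern, and both SAPs tie PDEV32 to Section 6.5.2. The P-gp inhibitor entry gives examples for a transporter interaction and does not set out to deal with QT. A careful reader who applies the opening clause arrives at the prohibition.

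Much of that stands. The prohibition is the better reading, and the Amendment 1 rationale in Appendix N, which describes the QTc appendix as a list of non-permitted drugs, supports it as the intent. But the opening clause qualifies the general permission. It does not cancel a later permission given by name, and criterion 15 works at entry only. What remains is a misleading named example on a safety point.

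It can also be said that the instruction to use caution covers the risk. Section 6.5.1 gives no reason for the caution. That it concerns P-gp is an inference from the subject of the entry and from the Amendment 4 rationale, which discusses raised tepotinib exposure. Either way, the entry does not tell a prescriber about QT, and caution is weaker than prohibition.

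**Conclusion.** The contradiction is real, narrow and worth correcting. It concerns one named drug, in current protocol text, and mainly affects drugs started on treatment. The existing QTc safeguards reduce the risk but do not remove it. The conclusion rests on reading the last entry of Section 6.5.2 as a ban on drugs, which its place in the non-permitted list and its reference to Appendix L make clear.

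A reader might infer three stronger things that the documents do not support:

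- *That subjects were harmed or wrongly withdrawn.* The documents give no frequency of clarithromycin use, so the number affected cannot be estimated.
- *That the primary result is affected.* Section 8.3.1 does count a subject without a qualifying scan at 12 weeks or later as not progression-free. With no frequency of use or of resulting withdrawals, however, no effect on the primary endpoint can be claimed.
- *That 1 of 11 measures the size of the problem.* It counts shared names in two lists of examples.

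**What to change.** Delete clarithromycin from the P-gp inhibitor examples in Section 6.5.1, and add a sentence that applies to the whole section:

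*Section 6.5.2 and Appendix L take precedence; any drug they cover remains prohibited even if it belongs to a class listed as permitted here.*

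The sentence should not be limited to P-gp inhibitors, because the substrate entry uses the same permissive wording and both lists are only examples.

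The cost is one word deleted, one sentence added and a notice to sites. A site notice alone is not enough: Section 10.5 requires protocol changes to be made by written amendment. The amendment may be classed as substantial, since Appendix N (Amendment 4) records that earlier edits to Sections 6.5.1 and 6.5.2 were redefined as substantial after a commitment to a national authority. It can be bundled with the next amendment. No extra patients, procedures or analyses are needed, and PDEV32 can stay as it is.

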### 6.5.2 Non-permitted Medicines

Any additional concomitant therapy that becomes necessary during the trial and any change to concomitant drugs must be recorded in the corresponding section of the eCRF, noting the name, dose, duration and indication of each drug.

The following are not permitted during the trial:

- Initiation of new interferon therapy for hepatitis within 30 days prior to Day 1 or at any time during the trial;
- Any other cancer therapy, including chemotherapy or local regional treatments, or any investigational product other than MSC2156119J as defined in this protocol;
- Prophylactic granulocyte colony stimulating factor (G-CSF) or granulocyte-macrophage colony stimulating factor (GM-CSF);

- Drug(s), for which the package insert/summary of product characteristics includes a contraindication for P-gp (e.g., dabigatran, aliskiren, colchicine), BCRP, and/or OCT1 inhibiting drugs, must not be combined with MSC2156119J;
- Drug(s) that are known to induce P-gp and thereby may decrease efficacy of MSC2156119J such as drugs known to induce P-gp (e.g., avasimibe, carbamazepine, phenytoin, rifampin, Saint John's wort);
- Subjects who receive a drug that is known to prolong QTc interval and cause respective cardiac side effects (see Appendix L).

Use of non-permitted medicines for any reason must result in withdrawal of the subject from this trial.

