# 6.5.3 Other Trial Considerations

If a subject undergoes non-permitted local-regional therapy during the trial (as described in the Exclusion Criteria; see Section 5.3.2), the subject must be withdrawn from the trial.

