### 7.1.5 Post-treatment Follow-up Visit

This visit will be performed  $30 \pm 3$  days after the last treatment for subjects who discontinue trial treatment permanently, including subjects who have completed an End of Treatment Visit. If another anticancer therapy will be started before the end of this period (30 days), the Post-treatment Follow-up Visit should be conducted prior to start of this therapy. Subjects who terminated their treatment early, for whatever reason, will be encouraged to return to the clinic for the Post-treatment Follow-up Visit. If the subject is unable to return for the Post-treatment Follow-up Visit, the reason should be clearly documented in the subject's medical record.

The following assessments and examinations will be performed on this day:

- Physical examination including body weight;
- ECOG PS;
- Vital signs;

Document No. CC

- ECG;
- Blood samples (to assess hematology, chemistry, and coagulation);
- Serum pregnancy test (if applicable);
- Urinalysis;
- AE assessment;
- Recording of concomitant medications/procedures;
- FHSI-8 and FACT-HP (Phase II only).

For operational purposes, a Trial Procedure Termination eCRF will be completed for all subjects when no further trial evaluations are expected (with the exception of potential survival follow-up). The following will be recorded in the eCRF: the date of discontinuation from trial procedures, the primary reason for discontinuation from trial procedures, and whether the subject agrees to be followed for survival.

Refer to Figure 4 for a schematic depicting when the Trial Procedure Termination eCRF will be completed. The Trial Procedure Termination eCRF will be completed at the Post-treatment Follow-up Visit for subjects who terminated their treatment due to disease progression, withdrawal of consent, loss to follow-up, or death. Subjects who discontinued trial treatment for all other reasons will continue to have tumor assessments according to the same schedule as subjects who remained on trial treatment. These assessments will continue until disease progression, withdrawal of consent, starting a new anticancer therapy, loss to follow-up, or death, at which time the Trial Procedure Termination eCRF will be completed.

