# 7.1.6 Survival Follow-up

Information about subject survival and anticancer therapies will be collected every 3 months  $(\pm 2 \text{ weeks})$  after End of Treatment until death, withdrawal of consent, or the end of the trial, whichever comes first. This information will be documented by the trial site personnel in the subject's source documents.

After discontinuation of survival follow-up, a Survival Follow-up Termination eCRF will be completed. The investigator must determine the primary reason for a subject's premature discontinuation from the trial and record this information on the Survival Follow-up Termination eCRF. For subjects who are lost to follow-up, the investigator should show due diligence by documenting in the source documents steps taken to contact the subject.

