12.1 Disposition of Subjects and Discontinuations

Analysis Set: Screening

Subjects will remain in the study until death, withdrawal of consent, or trial completion. Subjects are free to withdraw from the study at any time without giving their reason(s).

The following will be summarized for all screened subjects:

- Number of subjects screened (rescreened subjects will be counted once)
- Number of subjects rescreened
- Number of subjects who discontinued from the trial prior to treatment (overall and grouped by primary reason for discontinuation)
- Number and percentage of treated subjects. (i.e. those with at least one dose of trial treatment)
- Number and percentage of subjects who completed treatment (i.e. experienced death or disease progression)
- Number and percentage of subjects who discontinued treatment (overall and grouped by primary reason for discontinuation)
- Number and percentage of subjects who discontinued study procedures (overall and grouped by primary reason for discontinuation)
- Number and percentage of subjects who discontinued survival follow-up (overall and grouped by primary reason for discontinuation)

Percentages for the summaries above will be based on the ITT/SAF Analysis Set.

Number of subjects in the Screening Analysis Set along with number and percentage of subjects in the ITT/SAF and [SCI] Analysis Sets will be presented in a separate standalone summary.

The number and percentage of subjects from each region, country and clinical site will be summarized for the screening, ITT/SAF, and Analysis Sets.

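### Protocol 6.5.2 and 6.5.3 order withdrawal from the trial for events that 5.5.2 treats as reasons to stop MSC2156119J; read literally, they could end follow-up that the protocol means to continue

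*Protocol*

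**What the plan says.** Two sections order withdrawal from the trial. Protocol 6.5.2 gives a single consequence, not graded by drug: "Use of non-permitted medicines for any reason must result in withdrawal of the subject from this trial". Protocol 6.5.3 says that after non-permitted local-regional therapy "the subject must be withdrawn from the trial".

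Section 5.5.2, on withdrawal from MSC2156119J, covers the same ground differently. One bullet concerns a non-permitted drug under 6.5.2 "where the predefined consequence is withdrawal from MSC2156119J". Another covers starting any other anticancer treatment. Section 5.5.1, on withdrawal from the trial, makes only withdrawal of consent a mandatory reason.

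The follow-up rules after stopping the drug are these:

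- Protocol 5.5.2: "Subjects who discontinue trial treatment for reasons other than disease progression or withdrawal of consent will continue to have tumor assessments", on the schedule of those still treated. The end points are: "These assessments will continue until disease progression, withdrawal of consent, starting a new anticancer therapy, or death".
- Protocol 7.1.5, after naming progression, consent withdrawal, loss to follow-up and death: "Subjects who discontinued trial treatment for all other reasons will continue to have tumor assessments".
- Protocol 7.1.6: survival information is collected "after End of Treatment until death, withdrawal of consent, or the end of the trial".
- Phase II SAP 12.1: "Subjects will remain in the study until death, withdrawal of consent, or trial completion".

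Protocol 8.3.1 calls a Phase II subject progression-free only with an assessment of CR, partial response or SD at 12 weeks after the start of treatment or later. Every other case counts as not progression-free.

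**The concern.** The protocol gives withdrawal from the trial and withdrawal from the drug separate sections, and scheduled follow-up is set out for the second. Sections 6.5.2 and 6.5.3 use the first term for events that 5.5.2 files under the second, and the 5.5.2 cross-reference finds no matching text in 6.5.2. No passage reconciles them.

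Two sites could therefore handle the same event differently. Take a Phase II subject given ondansetron or azithromycin (both in Appendix L) at week 8. One site stops MSC2156119J and keeps scanning, and the subject may still be progression-free at week 12. Another withdraws the subject from the trial and stops scanning, and the subject is scored a failure whatever the tumor does. Survival contacts could be lost in the same way, which would shorten follow-up for OS, a descriptive secondary endpoint.

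**Working it through.** **Step 1. What each text requires, by type of event.**

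| Event | 6.5.2 / 6.5.3, literal | Scans under 5.5.2 and 7.1.5 | Survival contacts under 7.1.6 | At stake |
|---|---|---|---|---|
| Prohibited non-anticancer drug (P-gp inducer, QTc-prolonging drug, prophylactic G-CSF, new interferon) | Withdraw from trial | Continue | Continue | Scans and survival contacts |
| Other cancer therapy or local-regional therapy | Withdraw from trial | End at the new therapy | Continue | Survival contacts only |

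Section 5.5.2 does not cite 6.5.3 or name local-regional therapy. The match is through its bullet on other anticancer treatment and the local-regional treatments listed in 6.5.2.

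**Step 2. When the primary endpoint is affected.** All of the following must hold: the prohibited drug is not an anticancer therapy; the subject has no scan yet at 12 weeks or later; the site stops scanning; and no End of Treatment scan falls at 12 weeks or later. On the last condition, 5.5.1 asks for every effort to complete the End of Treatment investigations after withdrawal from the trial, and 7.1.4 includes a tumor assessment if the last was at least 6 weeks earlier. A subject withdrawn after a qualifying scan loses nothing on this endpoint.

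**Step 3. Reproduce the design.** Inputs from Protocol 8.1 and 8.5.2: n = 48, reject at 12 or more, null rate 0.15, alternative 0.30, one-sided 5%, power 80%. Exact binomial:

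- Type I error = P(X ≥ 12 | 48, 0.15) = 0.0478.
- Power = P(X ≥ 12 | 48, 0.30) = 0.8186.

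The plan's figures reproduce.

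**Step 4. Hypothetical size.** The documents give neither the number of subjects affected, k, nor their progression-free rate off drug, r. Both are assumptions here. Both readings stop the drug, so the right comparator is a subject off drug but still scanned.

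- Literal 6.5.2, with k forced failures: power = P(X ≥ 12 | 48 − k, 0.30).
- Scanning continued: power = P(A + B ≥ 12), with A ~ Bin(48 − k, 0.30) and B ~ Bin(k, r).
- Type I error with k forced failures = P(X ≥ 12 | 48 − k, 0.15).

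| k | Power, forced failures | Power if scanned, r = 0.15 | Loss (points) | Power if scanned, r = 0.30 | Loss (points) | Type I error, forced failures |
|---|---|---|---|---|---|---|
| 1 | 0.7940 | 0.8063 | 1.2 | 0.8186 | 2.5 | 0.0413 |
| 2 | 0.7672 | 0.7934 | 2.6 | 0.8186 | 5.1 | 0.0354 |
| 3 | 0.7380 | 0.7800 | 4.2 | 0.8186 | 8.1 | 0.0302 |

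At r = 0.15, part of the fall from 0.8186 comes from stopping the drug, which both readings require. Only the loss column belongs to the wording.

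**The case against.** The best case on the other side is that the protocol uses withdrawal from the trial loosely, and that the follow-up rules stand on their own.

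- Sections 5.1.2 (Phase II), 6.2 and 7.1.4 list withdrawal from the trial as a reason for ending treatment. The Treatment Duration part of 5.1.2 has much the same list with withdrawal from treatment. Section 6.2.3 also says withdrawn from the trial for a subject who cannot tolerate the lowest dose.
- The stop lists in 5.5.2, 7.1.5 and 7.1.6 do not include a withdrawal ordered by the protocol.
- Section 7.1.6 collects anticancer therapies after End of Treatment, so it expects subjects on new cancer therapy to remain in survival follow-up.
- Trial withdrawal necessarily includes stopping the drug, so the 5.5.2 cross-reference is imprecise rather than empty.

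Most of this stands. It makes stopping the drug only, with follow-up continued, the likely intent, and a site working from 7.1.5 and 7.1.6 would lose nothing. It does not remove the conflict, because 6.5.2 is phrased as an obligation and is the section a site consults when a prohibited drug has been given.

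A reader might infer more than the documents support:

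- That follow-up will be lost. It is one reading of 6.5.2, against several sections that point the other way.
- That every subject so withdrawn fails the primary endpoint. A qualifying scan already taken, or an End of Treatment scan at 12 weeks or later, prevents that.
- That local-regional therapy costs scans through this wording. Section 5.5.2 ends them there anyway.
- That the power loss is 2.5 to 8.1 points. That assumes subjects off drug keep the full 30% rate expected on treatment, which the documents do not support.
- That both SAPs back continued participation. Phase II SAP 12.1 does; Phase Ib SAP 12.1 ends it at progression or intolerable toxicity as well.

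**Conclusion.** The inconsistency is in the current text and should be corrected. It is a wording conflict between 6.5.2 and 6.5.3 on one side and 5.5.2, supported by 5.5.1, on the other. It does not show that the trial's follow-up fails.

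The exposure is avoidable missing data: survival contacts after any of these events, and tumor assessments after a prohibited non-anticancer drug. For the primary endpoint the direction is conservative: the 12-of-48 rule is unchanged and type I error falls from 4.8% to 4.1%, 3.5% or 3.0% with 1, 2 or 3 forced failures. The number of subjects cannot be derived from the documents. The loss of about 1.2, 2.6 or 4.2 points of power is a hypothetical that rests on an assumed count of 1, 2 or 3 and an assumed off-drug rate of 15%. No design figure needs to change.

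**What to change.** In Protocol 6.5.2 and 6.5.3, replace withdrawal from the trial with withdrawal from MSC2156119J. Add one sentence: tumor assessments continue under 5.5.2 and 7.1.5 unless a new anticancer therapy starts, and survival follow-up continues under 7.1.6. Point the non-permitted-drug bullet in 5.5.2 to that sentence. Leave the list of prohibited medicines and the periods over which they are prohibited as they are.

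The cost is wording only. The scans and the 3-monthly survival contacts are already in the schedule, and the sample size and decision rule stay the same.
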